This team member will be given 2 syringes.

- 1. a) The 50mL premixed syringe of papaverine as dispensed from pharmacy (NaCl 0.9% inj 48.8 mL + papaverine 6mg+ heparin 100 units)
- 2. b) 10 mL of 2 units/mL of heparin from the pressurized fast flush bag from the operating room.

Based on the list, one of the below will be aspirated in a Research syringe

- 3. 1) 2 mL from the premixed-papaverine syringe will be aspirated in a sterile aseptic fashion in a 3 mL BD syringe and labelled as RESEARCH SYRINGE, with patient identifiers, date and time of constitution, expiry time and signature.
- 4. 2) 2 mL of heparinized solution from the 2 units/mL heparin syringe will be aspirated in a 3 mL BD syringe and labelled as RESEARCH SYRINGE, with patient identifiers, date and time of constitution, expiry time and signature.

Time of administration: (see Figure 1: Flowchart)

The arterial catheters of all patients will be connected to the pressurized heparin flush system. All patients will receive 1 mL volume bolus from the "research syringe" as soon as the arterial catheter is placed and secured. Subsequent bolus from the "research syringe" will occur one hour after initial bolus.

 An intention to treat with 0.3 mg of papaverine (0.1mL from the papaverine vial) will be considered by the anesthesiology care team, if the arterial catheter spasm/patency or waveform does not improve 10 minutes after the second "research syringe" bolus (1 hour after initial placement).

[figure not shown]
[figure not shown]

[figure not shown]
Figure 1. Flowchart

Data Collected:

(Routine standard operating procedure data)

- 1. Patient Demographics
 - a. gestational age
 - b. age at operation
 - c. weight at birth
 - d. weight at operation
 - e. primary diagnosis
 - f. other diagnosis (syndrome, ductal dependency)
- 2. Operative Variable
 - a. type of surgery
 - b. duration of surgery
- 3. Arterial Catheters
 - a. time of placement

[figure not shown]
- b. site of catheterization
- c. number of attempts
- d. localization technique
- e. catheter placement technique
- f. Size and material type of the arterial catheter
- g. tubing length from the catheter to transducer
- Filtering set on arterial monitoring at a frequency higher than the natural frequency. For example, if patients heart rate is 70bpm, then a Filter frequency of (70*10)/60=11 Hz and above will be set. For a heart rate of 140bpm, a Filter of 20Hz will be set.

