- 4. Indicators of arterial waveform patency performed from baseline and then every 1 hour intraoperatively
 - a. color changes at catheter site (presence or absence of local axon reflex with fluid flushes after placement) when the arterial line is accessible
 - b. presence/ absence of a dicrotic notch (a distinct dicrotic notch implies system has good resolution at higher frequencies and is not overdamped)
 - c. ability to draw lab sample
 - i. Negative aspiration is easy and draws back freely without cavitation using a 3 mL BD syringe
 - ii. Negative aspiration is difficult (cavitation during negative aspiration, takes more than 30 seconds to draw 1 mL) using a 3 mL BD syringe
 - d. Square wave test-A fast flush system will be used. Pressure bag will be set to 300 mmHg and the resultant waveform will be recorded on paper
 - e. Presence of Oscillations- Yes/no, how many above baseline (there should be at least one bounce. If the system does not oscillate, then there is too much damping). There should be no more than two oscillations.
 - i. Amplitude of D1
 - ii. Amplitude of D12 (The amplitude of each oscillation is no greater than $\frac{1}{3}$ of previous oscillation)
 - iii. Arterial Blood pressure reading compared with NIBP measurement at times of measurement.
 - iv. Postoperatively, we will measure the duration of catheter patency (# hours/days) and the reason for discontinuation up to two days after the procedure.
- 5. Measurement of hemodynamics (HR, BP, ETCO2) before Papaverine/Heparin or Heparin bolus and at 1 min, 5min and 10 mins after bolus.

Primary Outcome:

1. Indicators of intraoperative arterial waveform patency as mentioned above in Data Collection section 4a to 4d

Data Handling and Record Keeping

All information will be kept strictly confidential and all data collection sheets will be kept in a binder which will be locked in the office of the principal investigator. A linking log will be

maintained to keep patient information separate from the data collection sheet. All data will be manually entered into a secure electronic database that will encrypted and password protected. (https://www.uth.edu/uthshare/)

Quality Control and Assurance

There are no plans to have ongoing third party monitoring. Data will be reviewed and audited internally to ensure that data is consistent, accurate and complete.

Sample Size:

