Since this is a pilot study, we will collect data on 50 patients in each group. Based on the Cohen's d for an anticipated effect size of 0.5 (we will use anyone of the indicators of patency as mentioned above), desired power level of 0.8 and a probability level of 0.05, we will re-submit for a full trial.

The list of potential patients will be obtained daily from the operating room log. Care4 records and OR Tracking will be used to screen for patients. The research team will make contact with the family member while obtaining the surgical and or the anesthesia consent.

Study Risks:

Papaverine acts on all smooth muscle cells and relieves vascular spasm. It is metabolized by the liver. There are no perceivable risks from exposure to papaverine bolus as it is standard of care to subject all patients in ICU to continuous infusion of papaverine after OR to maintain patency of arterial catheter and has been well studied in neonates and pediatric patients {Griffin:2005bo, Boris:1998wp, Heulitt:1993un}. Side effects of papaverine can include nausea, headache, flushing, bleeding, or allergic reaction. These side effects are rare.

Data and Safety Monitoring:

[figure not shown]
This study will not have a formal data and safety monitoring board. All subjects will be monitored by the Investigators for any adverse events, though none are anticipated. All unanticipated problems (adverse events, protocol deviations) will be reported to the IRB as required in a timely fashion.

Ethics:

We are seeking IRB approval for this study from CPHS.

Discussion of risks and possible benefits of participating in this study will be provided to the subjects and their families. Consent forms describing in detail the study procedures, and risks are given to the subject and written documentation of informed consent is required prior to starting the study.

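### The primary outcome is four unranked patency indicators read hourly, and the protocol leaves open which indicator and which hour will be used

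*Protocol*

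**What the plan says.** The Primary Outcome section of the protocol has one entry: "Indicators of intraoperative arterial waveform patency as mentioned above in Data Collection section 4a to 4d". Under Data Collected, item 4, these are:

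- 4a, colour change at the catheter site, read only "when the arterial line is accessible"
- 4b, whether a dicrotic notch is seen
- 4c, ability to draw a sample, easy or difficult; one criterion for difficult is that it "takes more than 30 seconds to draw 1 mL"
- 4d, the square wave test, recorded as a trace

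The heading of item 4 sets the schedule: "Indicators of arterial waveform patency performed from baseline and then every 1 hour intraoperatively". No indicator is ranked first, no composite is defined, and no time point or summary over the hours is chosen.

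The Sample Size section sets 50 patients per group because this is a pilot. It then gives an anticipated Cohen's d of 0.5, with the remark "we will use anyone of the indicators of patency as mentioned above", a power of 0.8, and "a probability level of 0.05, we will re-submit for a full trial".

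Under Time of administration, the second research bolus comes one hour after the first. Papaverine 0.3 mg is considered "if the arterial catheter spasm/patency or waveform does not improve 10 minutes after the second" research bolus.

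**The concern.** Naming the primary outcome and its time point is a protocol matter, so a statistical analysis plan that is not shown does not settle it. Nor is the protocol merely silent, since it says that any of the indicators will do.

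Two things are at stake. First, one 0.05 level holds for one comparison fixed in advance. It does not hold for the most favourable of several comparisons picked afterwards, and the Publication Plan intends peer-reviewed publication. Second, the hourly readings may not answer the same question. A reading taken before any rescue compares the research boluses. A later one may compare the groups after some patients in either group have received papaverine. As written, a reader cannot tell which comparison is primary.

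**Working it through.** **The plan's own figure.** With d = 0.5 and power 0.80, n per group = 2(z_alpha + z_power)² / d².

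- Two-sided 0.05: 2(1.960 + 0.842)² / 0.25 = 62.8, so 63.
- One-sided 0.05: 2(1.645 + 0.842)² / 0.25 = 49.5, so 50.

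The stated 50 thus matches a one-sided test, but the protocol states no sidedness and gives the pilot nature of the study as its reason for 50. The point below does not depend on the 50.

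**Inputs.** From the protocol: four indicators, level 0.05, 50 per group. Assumed, because the protocol gives none: two-sided tests, correlations between indicators, and event rates. The calculation supposes that the best of the four is picked.

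**Four exact 5% tests at one time point.**

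- Independent: 1 − (1 − 0.05)⁴ = 1 − 0.8145 = 0.185.
- Equal correlation ρ between the test statistics: 1 − ∫ [Φ((c − √ρ·z)/√(1−ρ)) − Φ((−c − √ρ·z)/√(1−ρ))]⁴ φ(z) dz, with c = 1.96.

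| ρ | False-positive rate |
|---|---|
| 0 | 18.5% |
| 0.3 | 17.4% |
| 0.5 | 15.6% |
| 0.7 | 13.0% |
| 0.8 | 11.4% |
| 0.9 | 9.4% |
| 1 | 5.0% |

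Items 4b to 4d read the same catheter system, so some positive correlation is likely. One-sided tests give similar figures: 16.4% at 0.3 and 10.6% at 0.8.

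**Binary indicators, 50 per group, event rates 10% to 50%.** Here the correlation is that of underlying normal variables. Item 4d is treated as yes/no for the calculation only, because it states no pass rule.

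- Fisher's exact test has a true size of 1.8% to 3.5%. Four independent tests give 1 − (1 − 0.0179)⁴ = 7.0% up to 1 − (1 − 0.0352)⁴ = 13.4%. At correlation 0.7 the range is 6.3% to 11.3%, and at 0.9 it is 5.2% to 9.4%.
- The uncorrected chi-square test has a true size of 5.0% to 5.7%. It gives 13.0% to 17.6% over correlations 0.9 to 0.7, and up to 20.9% if independent.
- If 4a is mostly unreadable, three indicators remain. Exact 5% tests give 14.3% (independent), 10.9% (0.7) or 8.4% (0.9). The mildest case (Fisher, correlation 0.9, event rate 10%) gives 4.3%, which is no excess.

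**If the hour is also chosen.** For exact 5% tests, with an assumed correlation of 0.3 to 0.8 between indicators and 0.5 to 0.8 between hours:

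| Hourly readings to choose from | False-positive rate |
|---|---|
| 2 | 17% to 30% |
| 3 | 21% to 39% |
| 4 | 24% to 47% |

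**Timing.** The second bolus is at 60 minutes, and 60 + 10 = about 70 minutes after the first bolus is when rescue is considered. Readings from about hour 2 can therefore follow papaverine in either group.

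**The case against.** The strongest reply is that this is a pilot with no stated test, success rule or alpha of its own. The 0.05 and the 0.8 stand in a sentence about returning with a full trial, the bracketed remark concerns an effect size, and a multiplicity rule may sit in a statistical analysis plan not shown. This stands as far as it goes, and it makes every error rate above conditional. It does not remove the defect, because the primary outcome itself is unfixed on the protocol's own words.

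Four stronger readings are tempting, but the document does not support them.

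- A reader might infer that the pilot will be called positive on any significant indicator. The protocol does not say so.
- A reader might infer that the full trial would be sized on an overstated effect, the largest of those observed. The Sample Size section names an anticipated d of 0.5 and does not say that an observed effect will be used.
- A reader might infer that the 1-hour reading is always free of rescue. Time of administration says when rescue is considered but does not bar earlier use. The account of current practice describes rescue whenever spasm is suspected. Nor is it stated whether the 1-hour reading falls before or after the second bolus, due at the same time.
- A reader might take 18.5% as a ceiling. It is one only for a single time point and tests of exact 5% size.

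**Conclusion.** The concern holds in this form: the protocol names four unranked primary indicators read at several hours and expressly leaves the choice among them open. That much rests on the text alone.

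The size is conditional on choosing after the data are seen. At one time point with exact 5% tests it lies between 5% and 18.5%, and is about 11% to 17% for assumed correlations of 0.8 to 0.3. A conservative test lowers it, in the mildest case to no excess at all, and free choice of hour raises it. Correlations and event rates are assumptions throughout.

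The difference in meaning between early and late readings is a possibility that the protocol should settle; the text does not show that the primary comparison is contaminated. This should be corrected, but since the study is a pilot with no stated confirmatory test, it is not fatal.

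**What to change.** In the Primary Outcome and Sample Size sections, replace the range 4a to 4d and the open choice of indicator with one named indicator at one time point, or one summary over the hours, fixed before unblinding. State where that reading falls relative to the second bolus and to rescue. Make the other indicators secondary and report them with intervals. If the named indicator is yes/no, as 4b and 4c are, express the sizing effect as a difference in proportions instead of Cohen's d.

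With one comparison fixed in advance, the 5% level holds. The cost is small: no new data or patients, but the sizing sentence must be rewritten, and a benefit seen only on another indicator or at another hour becomes supportive evidence. Keeping all four as primary with a Bonferroni split (0.05 / 4 = 0.0125 each, two-sided) would cost more. For d = 0.5 and 80% power it needs 2(2.498 + 0.842)² / 0.25 = 89.2, so 90 per group, and 50 per group would have about 50% power per indicator.
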